#### Data safety & Monitoring

Monitoring visits will be conducted by principle investigator, co- investigator as well as the representatives according to Guidelines for GCP. By signing this protocol, the investigator grants permission to the appropriate regulatory authorities to conduct on-site monitoring and/or auditing of all appropriate study documentation.

#### Subject Confidentiality

In order to maintain subject confidentiality, only a site number, subject number and subject initials will identify all study subjects on CRFs and other documentation submitted to the investigator. Additional subject confidentiality issues (if applicable) are covered in the Clinical Study Agreement.

#### Demographic and Baseline Characteristics

The following demographic variables at screening will be summarized by dose level: race, gender, age, height and weight.

## Data Analysis

Data will be analyzed by computer using SPSS software computer program. Descriptive statistical analysis including mean, medium, mode, standard deviation, percentage, frequenc will be analyzed by SPSS. Inferential statistics including chi-square test, t-tes, F-test, Anova, Correlation etc will also be done to find out existence of any significant relationship between variables of this study. An analysis plan will also be prepared considering objectives of the study. Different data will be presented in to the frequency tables, graphs, chart according to the requirements.

Study personnel at the site will enter data from source documents corresponding to a subject's visit into the protocol-specific paper CRF(Case report form). Subjects will not be identified by name in the study database or on any study documents to be collected by the principle investigator but will be identified by a site number, subject number and initials.

For paper CRFs: If a correction is made on a CRF, the study staff member will line through the incorrect data, write in the correct data and initial and date the change.

The Investigator is responsible for all information collected on subjects enrolled in this study. All data collected during the course of this study must be reviewed and verified for completeness and accuracy by the Investigator. A copy of the CRF will remain at the Investigator's site at the completion of the study (Annexure 3).

## **Ethical Issues and Implication**

This study will be approved by the BMRC, DGDA and the respective institution where the study will be taken place. Informed written consent of study populations will be taken. The study populations will be properly briefed about the risks and benefits of the study. None to minimum physical, psychological, cultural or financial harm of any kind is expected in the research work. If any adverse reaction on discomfort develop after applying one oro-nasal spray the individual participants will be provided with all necessary treatment without any cost in the respective hospital. The data will be coded and analyzed anonymously. The study will be conducted as per the Good Clinical Practice (GCP) and Good Laboratory Practice (GLP) guidelines applicable in Bangladesh and in accordance with the Declaration of Helsinki. All study information will be stored for twenty years and confidentiality of the study materials will be ensured. Necessary permission for data collection will be taken from respective hospital namely DMCH, KGH and KMH. Participants will have full right to participate or retract from the study at any level which will be well informed to the participants. The study will not have any ethical implication on the study subjects whatsoever. BMRC's Guidelines for Ethical Review of Projects involving Human Subjects has been carefully consulted in preparing this application for ethical clearance

## **Risk Management Plan**

PVP-I, the active ingredient of PONS oro-nasal spray assumes no potential threat to the subjects. It substantially retains the broad spectrum germicidal activity of iodine against the commonly encountered organisms in skin and wound infections, without the undesirable features or disadvantages of iodine. PVP-I is decisively microbicidal against all 4 (four) major classes of pathogens: bacteria (gram-positive and gram-negative, as well as antibiotic-resistant strains), fungi, viruses and protozoa. PVP-I is being used widely in various dosage forms such as eye drop preparation, ointment, mouthwash in much more higher concentration (4%, 1% etc.) for several decades [2-6]. So, PONS oro-nasal spray containing comparatively very low concentration (0.6% of PVP-I) which supposed to be safed in oro-nasal application. Moreover, this oro-nasal spray is intended to be used in the selected hospitalized patients under the direct supervision of doctors &

nurses only volunteer will be healthy one who will also be remained is close supervision of physicians and researcher. Therefore, any adverse reaction risk if arises will be managed accordingly with the available facilities in respective hospital without any cost.

- If any discomfort, irritation, burning sensation occur then nasal irrigation with sterile plan water by 50 cc disposable syringe is to be given.
- If any hypersensitivity reaction occurs then anti-histamine and/or steroid is to be given

#### • Clinical Laboratory Measurements

#### Blood Chemistry Profile

Blood sample for Group - C participants will be collected and sent to the respective hospitals/BRICM clinical chemistry lab for determining of TSH, FT3, FT4, Serum creatinine, alanine aminotransferase (ALT/SGPT) level including urine test.

# • Facilities: (Resources, equipment, chemicals, subjects (human, animal) etc. required for the study):

Existing facilities of Dhaka Medical College Hospital, Kurmitola General Hospital, Kuwait-Moitree Hospital and Bangladesh Reference Institute for Chemical Measurements will be utilized human subjects will be randomly selected for three hospital after getting proper written comments.

## Endpoints

#### **Primary Endpoints:**

• Virucidal efficacy of 0.6% PVP-I against SARS-COV-2 virus which infect oropharyngeal and nasopharyngeal mucosa of humans.

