## **Research Question**

- Does 0.6% PVP-I containing oronasal spray kill or reduce spread transmission of SARS-CoV-2 virus residing on nasopharynx and oropharynx of healthy person or healthy carrier before and after exposed to COVID-19 case?
- Does 0.6% PVP-I containing oronasal spray could be safely used amongst healthy individual

or healthy carrier?

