## **Objectives of the study**

#### a. Primary Objective

To assess the virucidal efficacy of 0.6% PVP-I against SARS-CoV-2 in nasopharynx and oropharynx in order to use:

- To prevent viral infection before exposure while visiting and treating COVID-19 patients, attending public gatherings, using public transport etc.
- To prevent viral infection after exposure to COVID-19 patients
- To reduce viral load in nasopharynx and oropharynx of COVID-19 patients which is supposed to reduce viral transmission through respiratory route

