#### b. Secondary Objectives

- To assess the viral load in the nasopharynx and oropharynx before and after application of 0.6% PVP-I of participants of this study.
- To assess the duration of effectivity of 0.6% PVP-I on mucosal surface of participating COVID-19 patients by testing consecutive sample hourly upto 4hr.
- To estimate the shelf-life and stability of 0.6 % PONS.
- To characterize raw materials and impurities for product development and quality control/ assurance
- To measure the safety level of  $0.6\% \underline{PONS}$  by biochemical analysis of participants blood & urine

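### The primary endpoint is virucidal efficacy, but RT-PCR is the only virological measurement: the trial can show a difference in detectable viral RNA, not killing, and no group can show prevention of infection

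*Protocol*

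**What the plan says.** **What is claimed.** Protocol, Primary Endpoints, gives "Virucidal efficacy of 0.6% PVP-I against SARS-COV-2 virus which infect oropharyngeal and nasopharyngeal mucosa of humans", with no variable, time point or threshold. The Primary Objective is "To assess the virucidal efficacy of 0.6% PVP-I against SARS-CoV-2 in nasopharynx and oropharynx in order to use", followed by three bullets. Two concern uninfected people: "To prevent viral infection before exposure while visiting and treating COVID-19 patients" (and in other public settings) and "To prevent viral infection after exposure to COVID-19 patients". The third concerns patients: "To reduce viral load in nasopharynx and oropharynx of COVID-19 patients which is supposed to reduce viral transmission through respiratory route". The Research Question asks "Does 0.6% PVP-I containing oronasal spray kill or reduce spread transmission of SARS-CoV-2 virus", with the virus described as "residing on nasopharynx and oropharynx of healthy person or healthy carrier before and after exposed to COVID-19 case". The Study Rationale closes by naming virucidal efficacy in humans as the aim. The Summary allows for a preventive effect being proved by this study, and Utilization of Results would encourage public use for prevention.

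**What is measured.** Under Study design:
- Group A (384 per arm) receives one application of 0.6% PVP-I or distilled water, waits 2-5 minutes, and is swabbed for RT-PCR.
- Group B (20 patients, no control arm) has hourly RT-PCR for four hours after one application.
- Group C (10 healthy users, no control arm) gives blood and urine on days 0, 10, 20 and 30.

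The N.B. after Study design explains that Ct is semiquantitative and tracks viral genetic material. Among the Secondary Objectives are "To assess the viral load in the nasopharynx and oropharynx before and after application of 0.6% PVP-I of participants of this study" and a duration-of-effect aim. The SAP contains a sample-size formula and a list of tests; it defines no endpoint.

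**The concern.** RT-PCR amplifies RNA. It does not say whether the virus that carried the RNA could still infect. A primary conclusion about killing therefore does not follow from the planned data, even with perfect conduct, and the inference fails in both directions. Similar Ct values in the two arms would not show that the spray failed to kill. A clear difference would show less detectable RNA, but not the fraction killed or any loss of infectiousness.

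Prevention is a further step away, because no participant is observed for acquiring infection. What is at stake is public advice: Utilization of Results would turn the finding into encouragement to use the spray for protection.

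**Working it through.** **1. Match each claim to its measurement.**

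| Claim (Protocol section) | Measurement available | What it can support |
|---|---|---|
| Virucidal efficacy, kill (Primary Endpoints, Primary Objective, Research Question, Study Rationale) | Group A RT-PCR, 2-5 minutes after spraying | Between-arm difference in detectable RNA |
| Lower viral load in patients (third bullet of Primary Objective) | Same | Yes, as RNA load |
| Viral load before and after (Secondary Objectives) | Group A steps list a post-spray swab only | Between-arm comparison, unless a pre-spray Ct exists elsewhere |
| Duration of effect (Secondary Objectives) | Group B hourly RT-PCR, uncontrolled | Course of detectable RNA |
| Prevention (Summary, Research Question, Utilization of Results) | None | Nothing |

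**2. Who could show prevention?** The inclusion criteria for Groups A and B require a positive RT-PCR in the preceding 24 hours. That covers 384 + 384 = 768 patients, or 768 + 20 = 788 if Group B is separate from Group A. Group C starts uninfected, but Study design and Blood Chemistry Profile list only biochemistry and urine tests. Adding an infection test would not repair this: zero infections in 10 leaves a two-sided 95% upper limit of 1 - 0.025^(1/10) = 0.31, with no comparator.

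**3. Can Ct be converted into killing?** Mode of Action gives nucleic-acid oxidation as well as protein and membrane damage, so RNA is at most a partial proxy. As an illustration, take the 99.99% kill that the Summary cites, assume one doubling per cycle, and let f be the share of killed virus whose RNA still amplifies. The documents give no value for f. The Ct shift is -log2(1 - 0.9999 × (1 - f)):
- f = 0: 13.3 cycles
- f = 0.1: 3.3 cycles
- f = 0.5: 1.0 cycle

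The same kill is compatible with very different Ct shifts. This shows that killing cannot be recovered from Ct; it does not estimate the size of any error.

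**4. Does the present sample serve the restated endpoint?** The plan's own figure reproduces: 1.96² × 0.5 × 0.5 / 0.05² = 384.16, stated as 384. It is a precision figure for one proportion: 1.96 × √(0.25/384) = 0.050. For a difference between two arms of 384 with a common proportion p, the 95% half-width is 1.96 × √(2p(1-p)/384):
- p = 0.5: 0.071
- p = 0.2: 0.057
- p = 0.1: 0.042

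The proportion undetectable is not given in the documents, so p is an assumption; 0.5 is the widest case.

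**The case against.** The proxy is disclosed: the N.B. after Study design says openly what Ct measures. Mode of Action makes a Ct change plausible, and RT-PCR suits the viral-load aims. All of that stands. It means RT-PCR is a reasonable test for a viral-load question. It does not supply a link from Ct to loss of infectivity, and the endpoint is not worded as viral load.

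The prevention bullets can also be read, by their grammar, as intended uses of a virucidal product, and Primary Endpoints does not mention prevention. That also stands. A reader might infer that prevention is a formal primary endpoint left unmeasured, but the documents do not go that far. The difficulty lies in the Summary, the Research Question and Utilization of Results, which attach a prevention conclusion to the study.

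On baseline, the qualifying RT-PCR precedes the spray, and Group B's numbering of second to fourth samples implies a first sample of unstated timing. Neither is said to supply a baseline Ct. The before-and-after aim therefore needs clarification; it cannot be called impossible.

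Finally, a reader might go further and say that spray residue in a swab taken 2-5 minutes later invalidates the PCR. The documents describe no check for carry-over, and a distilled-water control does not exclude assay interference by PVP-I. They also give no evidence that interference occurs. It is a limitation to declare.

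**Conclusion.** The mismatch is real and should be corrected before results are reported. The stated primary conclusion, killing, cannot be drawn from RT-PCR alone, and no group yields evidence on prevention of infection. This rests on the absence of any infectivity test or infection outcome in the protocol and SAP as supplied.

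It has no size in points or cycles, because it concerns what the result means. Two stronger readings are not supported. A reader might infer that the Group A comparison is worthless, but a randomised comparison of detectable RNA remains interpretable as that, subject to the residue caveat. A reader might also infer that the endpoint needs more patients or a different type of test. The plan is sized on a proportion and already lists chi-square, and 384 per arm estimates the difference in proportion undetectable to within about ±7.1 points at worst. The documents state no target difference against which to call that too wide or adequate.

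**What to change.** 1. In Primary Endpoints and in the SAP, define the primary endpoint as SARS-CoV-2 RNA by RT-PCR in the Group A swab taken 2-5 minutes after one application, 0.6% PVP-I versus distilled water, with all randomised patients analysed as allocated. Report the between-arm difference in proportion undetectable with a 95% CI and the chi-square test already listed in Data Analysis and SAP section 2. Give Ct as a supporting result.
2. In Research Question, Primary Objective, Study Rationale (the aim sentence) and Primary Endpoints, replace the virucidal and kill wording with *reduction in RT-PCR-detectable viral RNA*. Word the Group B duration objective the same way.
3. Mark the two prevention bullets as future use, and limit the Summary, Research Question and Utilization of Results to match. State that infectivity, transmission and prevention are not measured, and that spray residue in the swab could contribute to a PCR difference because no check for it is described.
4. Clarify whether the qualifying RT-PCR or a first Group B sample supplies a pre-spray Ct. If neither does, word the before-and-after objective as a between-arm comparison for Group A.

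The cost is a weaker headline claim and some redrafting, with no extra patient, swab or assay. Keeping the word virucidal would instead require an infectivity test, which neither document describes.

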#### Secondary Endpoints:

- Patient is to be safe with no significant side effect after using this oronasal spray.
- Safe if participants of the study who will use 0.6% PONS with minimum side effect (if any)

## Sponsoring agency

**BRICM will be the sponsoring agency of this research work**. BRiCM, said to be the producer of proposed PONS Oro-nasal Spray containing 0.6% PVP-I, is a statutory body functioning under the administrative control of the Ministry of Science and Technology. It is basically a research organization and a reference institute in the area of chemical measurements. It is neither a commercial enterprise nor a profit making organization. According to constitutional sanction the principal responsibility of BRiCM is to carry on research leading to such innovation that will add value to the government effort for ensuring welfare of the people.

Worth mentioning that, undertaking R&D program targeting to improvement of the quality of life of the people is one of the prime functions of a research laboratory like BRiCM. It is well equipped with necessary state of the art equipment, skilled manpower (scientists and logistic support staff) and adequate fund for implementation of R&D program either by itself or in collaboration with others. So, it is within the scope of BRiCM to undertake the proposed R&D, in collaboration with Dhaka Medical College Hospital, from its own budget which is provided by the government.

The proposed product cannot be considered as a commercial one and BRiCM is not the commercial producer. Rather, BRiCM takes the responsibility to develop it as a laboratory product ensuring appropriate quality as mentioned in Annexure-C (rephrased), the Methodology and Study design

Section meeting compliance requirements, especially targeting to ease the severity of the current pandemic situation in the country.

Besides, the clinical trial will be conducted in the hospitals, independent of BRiCM, under the general the guidance of BMRC, wherein, BRiCM will not have any role in decision making and the efficacy of the product will be finally determined by BMRC. Hence, funding by BRiCM for proposed PONS Oro-nasal Spray cannot give rise to the question of conflict of interest.

#### N.B.

The researchers and supporting persons those are directly involved in the hospital work with patient service; their effort should be awarded by honorarium, depicted in the Annexure E. Moreover, researcher and supporting stuff those who have to come in direct contact/exposure to COVID-19 patient which involve huge risk. The honorarium should be considered as source of encouragement of this novel task.

## **Utilization of Results**

By providing information and assurance about the efficacy and safety of 0.6% PVP-I, we can inform and encourage people to use it as oronasal spray safely for prevention of COVID-19, as an adjunct to PPE and reduce transmissibility of SARS Cov-2 virus. The safe use of oronasal spray cumulatively will provide very significant impact on COVID-19 prevention inside the country as well as over global population which is expected to contribute to save lives in this COVID-19 pandemic situation.

#### References: Vancouver style will be followed.

Ethical approval for the study will be taken from BMRC

• Approval / Forwarding of the Head of Department / Institute / IRB.

# **Schedule of Activities (Flow Chart)**

# Feb 2021- June 2021

Events	February	March	April	May	June
Topic selection and					
submission of protocol					
Approval of protocol					
Planning and designing					
Literature review					
Preparation of questions					
Data collection field preparation					
Data processing and analysis					
Report writings and editing					
Submission of report					

NB: All stages of the main task supervision committee will be consulted.

## Statistical Analysis Plan (SAP)

## 1. Sampling Technique

Sample Size

• The minimum sample size is given by:

Where, n= sample size Z = Standard normal deviate usually set at 1.96 at 95% confidence If prevalence is not known, the value of prevalence will be considered as 50%.

So, p will be 0.5.

So, q = (1-p) = 0.50, and

d = Desired accuracy or degree of allowable error. It is usually set as 5%(0.05).

So, n = { $(1.96)2 \ge 0.5 \ge 0.5$ } / (0.05)2

Or, n = 384

for a finite population  $n = (Z2 \times p \times q) / d2$ 

N.B. Calculated sample size is equally applicable for both experimental (Intervention) and control group.

## 2. Statistical Analysis tools

Data analysis software	: Statistical Package for the Social Sciences (SPSS)
Descriptive statistical parameter	: Mean, Medium, Mode, Standard Deviation, Percentage,
	Frequency
Inferential statistics	: Chi-square test, t-tes, F-test, Anova, Correlation
Confidence Interval	: 95%
